2. REVISION HISTORY

Version	Date	Action	Performed by
	(dd/MMM/yyyy)		
00	13-Aug-2017	Initial Release	[name]
01	09-Oct-2017	Protocol revision no change to SAP	[name]

4. LIST OF ABBREVIATIONS AND DEFINITIONS OF TERMS

4.1 Abbreviations

AAA Abdominal Aortic Aneurysm

ABI Ankle Brachial Index
ACT Activated Clotting Time

AE Adverse Event
A-P Anteroposterior

BARC Bleeding Acadamic Research Consortium

BAV Balloon aortic valvulopasty

BP or bp Blood Pressure

CIP Clinical Investigation Plan

CRF Case Report Form

CRO Contract Research Organisation

DSMC Data Safety Monitoring Committee

EC European Commission

eCRF Electronic Case Report Form
EDC Electronic Data Capturing

EEC European Economic Community

EN European Norm (European Standard)

EU European Union

EVAR Endovascular Aortic Aneurysm Repair

F French gauge

GP General Practitioner

Hb Haemogloben
HR or hr Heart Rate

ICF Informed Consent Form IFU Instructions for Use

IS Irish Standard

ISO International Standards Organisation

ITT Intent-toTreat

LVAD Left ventricular assist device

M-L Mediolateral mITT modified ITT

OPT Overall Procedural Time

PDO Polydioxanone

PDS Polydioxanone suture
PIS Patient Information Sheet

PP Per-Protocol

PSR Procedure Success Rate

RBC Red Blood Cell

SADE Serious Adverse Device Effect

SAE Serious Adverse Event SVD Source Data Verification

TAVI Transcatheter Aortic Valve Implantation
TAVR Transcatheter Aortic Valve Replacement

TEVAR Thoracic Endovascular Aortic/Aneurysm Repair

TSR Technical Success Rate

TTA Time to Ambulation
TTD Time to Discharge

TTDD Time to Device Deployment

TTH Time to haemostasis

U Units of Blood (1 pint or 450 ml)

USADE Unanticipated Serious Adverse Device Effect

VARC Valve Academic Research Consortium

VCD Vascular Closure Device
WMA World Medical Association

4.2 Definitions of terms

- Pulse Grading System The peripheral pulse pressure shall be indicated using the following grading:
 - 0 Absent
 - 1 Diminished/weak
 - 2 Normal
 - 3 Strong
- ii. **Major Vascular Access Site Complication** In the context of this CIP and related to the femoral artery access site, major complications* are any of:
 - Major vascular access site complications leading to death, life-threatening (BARC type 5)
 or major bleeding (BARC type 3a), visceral ischemia or neurological impairment; OR
 - Distal embolization from the vascular access site requiring surgery or resulting in amputation or irreversible end-organ damage; OR
 - The use of unplanned endovascular or surgical intervention associated with access site related death, major bleeding (BARC type 3a), visceral ischemia or neurological impairment; ORleading to death, life-threatening or major bleeding*, visceral ischaemia or neurological impairment.

- Any access site related new ipsilateral lower extremity ischemia documented by patient symptoms, physical exam, and/or decreased or absent blood flow on lower extremity angiogram; OR
- Surgery for access site-related nerve injury; OR
- Permanent access site-related nerve injury; OR
- Access-site-related infection requiring intravenous antibiotics and/or extended hospitalization
- * Adapted from VARC-21.
- iii. **Minor Vascular Access Site Complications** In the context of this CIP and related to the femoral artery access site, minor complications* are any of:
 - Access site or access-related vascular injury
 - Dissection
 - Stenosis
 - Perforation
 - Rupture
 - > Arteriovenous fistula
 - Pseudoaneurysm (> 3 cm)
 - > Haematoma (> 6 cm)
 - Percutaneous closure device failure

not leading to death, life-threatening or major bleeding (BARC type 3a), visceral ischaemia or neurological impairment.

- Distal embolization from the vascular access site treated with embolectomy and/or thrombectomy and not resulting in amputation or irreversible end-organ damage.
- Localized access site infection treated with intramuscular or oral antibiotics.
- Any access site related unplanned endovascular stenting or unplanned surgical intervention not meeting the criteria for a major vascular complication.
- Access site related vascular repair or the need for vascular repair (via surgery, ultrasoundguided compression, transcatheter embolization, or stent graft)
- Failure of a closure device to achieve haemostasis at the arteriotomy site leading to alternative treatment (other than manual compression or adjunctive endovascular ballooning)

¹ Kappetein AP, Head SJ, Généreux P, et al. Updated standardized endpoint definitions for transcatheter aortic valve implantation: the Valve Academic Research Consortium-2 consensus document. European Journal of Cardio-Thoracic Surgery 42 (2012) S45–S60 (Ref. 6).

iv. BARC Bleeding Definitions (Ref. 7)

Life-threatening or disabling bleeding

- Fatal bleeding (BARC type 5) OR
- Bleeding in a critical organ, such as intracranial, intraspinal, intraocular, or pericardial necessitating pericardiocentesis, or intramuscular with compartment syndrome (BARC type 3b and 3c) OR
- Bleeding causing hypovolemic shock or severe hypotension requiring vasopressors or surgery (BARC type 3b) OR
- Overt source of bleeding with drop in haemoglobin of ≥5 g/dL or whole blood or packed red blood cells (RBCs) transfusion ≥4 units* (BARC type 3b)
 - *Given one unit of packed RBCs typically will raise haemoglobin concentration by 1 g/dL, an estimated decrease in haemoglobin will be calculated.

Major bleeding (BARC type 3a)

- Overt bleeding plus haemoglobin drop of 3.0 g/dL to ≥5 g/dL (provided haemoglobin drop is related to access site bleed); AND
- Does not meet criteria of life-threatening or disabling bleeding

Minor bleeding (BARC type 2 or 3a, depending on the severity)

- Any bleeding worthy of clinical mention (e.g. access site haematoma) that does not qualify as life-threatening, disabling, or major bleeding.
- v. Haemostasis Clinically acceptable cessation of arterial bleeding.

vi. Study Variables:

- a. Have a direct impact on claims for the device.
- b. Should be directly observable.
- c. Objectively determined measures subject to minimal bias and error.
- d. Should be directly related to biological effects of the clinical condition.

vii. Influencing Variables:

- a. Any aspect of the study that can affect the outcome or study variables.
- b. Any aspect of the study that can affect the relationship between treatment and outcome.
- viii. **Device Failure** Failure of the PerQseal® to provide percutaneous access site closure resulting in interventional (e.g. stent-graft) or surgical correction.

^{*} Adapted from VARC-21

- ix. **Time to Haemostasis** Time to haemostasis (TTH) is determined as the elapsed time from when the Introducer-sheath and PerQseal® closure device have been removed from the patient to first observed cessation of bleeding (excluding cutaneous or subcutaneous oozing) at the target access site arteriotomy.
- x. **Time to Ambulation** Time to Ambulation (TTA) is defined as the time from post procedure sheath removal until the patient is comfortable walking approximately 6 m.
- xi. **Time to Device Deployment** Time to Device Deployment (TTDD) is defined as the time from insertion of the PerQseal[®] closure device into the Introducer-sheath to complete removal of the PerQseal[®] closure device and Introducer-sheath from the patient following deployment.
- xii. **Overall Procedural Time** Overall Procedural Time (OPT) is defined as the time from first invasive contact with the patient's groin to completion of all aseptic procedures related to the groin.
- xiii. **Technical Success Rate** Technical Success Rate (TSR) is defined as the number of PerQseal® closure devices that are deployed and achieve haemostasis (i.e. cessation of bleeding (excluding cutaneous or subcutaneous oozing)) without need for any alternative treatment (other than manual compression or adjunctive endovascular ballooning) at target access site, divided by the total number of PerQseal® closure devices where deployment was attempted (as per the PerQseal® closure device IFU). Device malfunction resulting in alternative therapy will be considered as a technical failure.
- xiv. **Surgical Closure** Standard surgical vascular access and sutured closure.
- xv. **Baseline** Prior to interventional procedure.
- xvi. **Endovascular Aortic/Aneurysm Repair (EVAR)** Endovascular surgery used to treat an abdominal aortic aneurysm (AAA).
- xvii. **Thoracic Endovascular Aortic/Aneurysm Repair (TEVAR)** Endovascular surgery used to treat a Thoracic aortic aneurysm.
- xviii. **Transcatheter Aortic Valve Replacement (TAVR)** Procedure in which a bioprosthetic valve is inserted through a catheter and implanted within the diseased native aortic valve. Also known

as Transcatheter Aortic Valve Implantation (TAVI) or Percutaneous Aortic Valve Replacement (PAVR).

- xix. **Activated Clotting Time (ACT)** Measures the intrinsic clotting activity of whole blood in seconds.
- xx. **Source Data Verification (SDV)** Evaluation of the conformity of the data presented in eCRFs with source data (medical records/notes, lab results, x-rays, etc.).
- xxi. **Ankle-brachial index (ABI)** The ratio of ankle systolic pressure to the arm systolic pressure, used in assessing the status of lower extremity arteries. It is calculated by dividing the higher of the left and right ankle pressures by the higher of the two brachial artery pressures.
- xxii. Time from PerQseal[®] Introducer insertion to PerQseal[®] closure device deployment defined as the time from insertion of the PerQseal[®] Introducer to complete removal of the PerQseal[®] closure device and Introducer-sheath from the patient following deployment.

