- Bleeding causing hypovolemic shock or severe hypotension requiring vasopressors or surgery (BARC type 3b) OR
- Overt source of bleeding with drop in haemoglobin of ≥5 g/dL or whole blood or packed red blood cells (RBCs) transfusion ≥4 units* (BARC type 3b)

Major bleeding (BARC type 3a)

- Overt bleeding plus haemoglobin drop of 3 to <5 g/dL (provided haemoglobin drop is related to bleed); AND
- Does not meet criteria of life-threatening or disabling bleeding.

Minor bleeding (BARC type 2 or 3a, depending on the severity)

• Any bleeding worthy of clinical mention (e.g. access site haematoma) that does not qualify as life-threatening, disabling, or major bleeding.

Technical Success Rate – Technical Success Rate (TSR) is defined as the number of PerQseal® closure devices that are deployed and achieve haemostasis (i.e. cessation of bleeding (excluding cutaneous or subcutaneous oozing)), without need for any alternative treatment (other than manual compression or adjunctive endovascular ballooning) at target access site, divided by the total number of PerQseal® devices where deployment was attempted (as per the PerQseal® closure device IFU). Device malfunction resulting in alternative therapy will be considered as a technical failure.

REVISION	DCN				
AA	2772				
AB	2966				

² Kappetein AP, Head SJ, Généreux P, et al. Updated standardized endpoint definitions for transcatheter aortic valve implantation: the Valve Academic Research Consortium-2 consensus document. *European Journal of Cardio-Thoracic Surgery* 42 (2012) S45–S60.

^{*}Adapted from VARC-22.

^{*}Given one unit of packed RBCs typically will raise haemoglobin concentration by 1 g/dL, an estimated decrease in haemoglobin will be calculated.

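### The transfusion correction is not tied to the major-bleeding threshold, so bleeds given 1 to 3 units can be graded minor and leave the primary endpoint

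*SAP*

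**What the plan says.** The bleeding grades are set out in SAP 4.2 iv and in the protocol's Definitions, under BARC Bleeding Definitions.

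- **Life-threatening or disabling.** One criterion reads "Overt source of bleeding with drop in haemoglobin of ≥5 g/dL or whole blood or packed red blood cells (RBCs) transfusion ≥4 units". The asterisk sits at the end of that line, on the unit count. Its note reads "Given one unit of packed RBCs typically will raise haemoglobin concentration by 1 g/dL, an estimated decrease in haemoglobin will be calculated". The protocol places the asterisk on the same criterion, and its note also ends "an estimated decrease in haemoglobin will be calculated".
- **Major.** SAP: "Overt bleeding plus haemoglobin drop of 3.0 g/dL to ≥5 g/dL (provided haemoglobin drop is related to access site bleed); AND". Protocol: "Overt bleeding plus haemoglobin drop of 3 to <5 g/dL (provided haemoglobin drop is related to bleed); AND". In both documents a second condition follows; in the SAP it is "Does not meet criteria of life-threatening or disabling bleeding". Neither version of the major criterion carries the asterisk, a unit count or a reference to an estimated drop.
- **Minor.** This is the residual grade: any bleeding worth recording "that does not qualify as life-threatening, disabling, or major bleeding". Its heading begins "Minor bleeding (BARC type 2 or 3a, depending on the severity", so the label 3a is attached to both the major and the minor grade.

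Major bleeding enters the primary endpoint through the definition of a major vascular access site complication (SAP 4.2 ii and the protocol's Definitions), where it is identified by the label 3a. SAP 11.6 counts only device-related complications up to 1 month.

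**The concern.** Transfusion raises haemoglobin, so a measured drop understates the blood lost. The plan recognises this, but it marks the correction at four or more units, where the unit count alone already makes the bleed life-threatening. The correction decides the grade at 1 to 3 units, around the 3 g/dL threshold, and there the text is silent.

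If the threshold is applied to the measured drop, some transfused bleeds fall to minor. The shift goes one way: it can only remove events from the primary count, and a lower count favours non-inferiority. The label 3a does not settle the question, because it names both grades.

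**Working it through.** **Planning context.** The plan gives no figure for this bleeding question. Its related figure is 68 closures (SAP 10: limit 0.17, assumed rate 5%, one-sided 0.025, power 90%). The arcsine formula gives n = [(1.960 + 1.282) / (2·asin√0.17 − 2·asin√0.05)]² = 66.02, rounded up to 67, which is close to 68. That figure is not at issue here. Below, n = 75 (planned enrolment) and the limit is 0.17.

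**Step 1: which bleeds change grade.** Estimated drop = measured drop + 1 g/dL × units. The literal reading uses the estimated drop within the life-threatening criterion that carries the asterisk, and the measured drop for the 3 g/dL threshold.

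| Units | Measured drop (g/dL) | Estimated drop (g/dL) | Literal grade | Grade on estimated drop |
|---|---|---|---|---|
| 1 | 2.0 to <3.0 | 3.0 to <4.0 | minor | major |
| 2 | 1.0 to <3.0 | 3.0 to <5.0 | minor | major |
| 3 | 0 to <2.0 | 3.0 to <5.0 | minor | major |
| 4 or more | any | not needed | life-threatening | life-threatening |

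Untransfused bleeds are unaffected. The literal reading also skips a grade. After 3 units, a measured drop of 1.9 (estimated 4.9) is minor, while 2.0 (estimated 5.0) is life-threatening.

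**Step 2: the SAP's upper end.** A drop of ≥5 g/dL meets the life-threatening criterion, and the second condition on major bleeding then excludes it from major. Replacing ≥5 with <5 changes no grade.

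**Step 3: the decision cut-off.** The exact upper bound for x events in 75 is the (1 − α) quantile of Beta(x + 1, 75 − x). SAP 11.6 gives two levels, a one-sided 95% bound and a one-sided 0.025 test, so both are shown.

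| One-sided α | Passes | Fails |
|---|---|---|
| 0.025 | 6 events, bound 0.166 | 7 events, bound 0.183 |
| 0.05 | 7 events, bound 0.168 | 8 events, bound 0.184 |

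At the planned 5% rate, 75 × 0.05 = 3.75 events are expected. The chance that the true count is exactly one above the cut-off is 0.966 − 0.919 = 0.047 for 7 events, and 0.021 for 8.

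**Step 4: size if events are lost.** The documents give no frequency, so assume that a fraction f of all true primary events is lost. At a true rate of 0.17, the chance of passing is P(X ≤ cut-off) with X ~ Binomial(75, 0.17 × (1 − f)).

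| f (assumed) | α = 0.025 (≤6 events) | α = 0.05 (≤7 events) |
|---|---|---|
| 0 | 2.0% | 4.6% |
| 10% | 4.7% | 9.6% |
| 20% | 10.1% | 18.3% |
| 30% | 19.7% | 31.8% |

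Bleeding is only one route into the endpoint, so f is a share of all events, not of bleeds. The table shows sensitivity and is not a forecast.

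**The case against.** The footnote is unqualified. It says that an estimated decrease will be calculated, and nothing confines that estimate to one grade. Because the asterisk sits where the correction is least needed, the note can fairly be read as the general way to derive any haemoglobin drop. This stands: the documents leave the scope open and do not exclude the major grade. It does not remove the problem, since two adjudicators following the text could grade the same bleed differently.

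A bleed graded minor may still count through another major criterion, such as limb ischaemia, and only device-related events count. The SAP also plans adjudication (List 6 records device relation, severity and type of complication). These points limit the effect, but neither document gives the adjudicators a rule for 1 to 3 units.

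The one-event comparison describes the boundary only. Any change of definition matters when the count sits there, and at the planned rate that is unlikely (0.047 or 0.021).

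A reader might infer from the SAP's ≥5 that major and life-threatening bleeding overlap and that patients would be misgraded. The documents do not support this: the second condition on major bleeding resolves the overlap. The sign may also be a character fault in the file, although it reads sensibly elsewhere in the section. Nor does this slip cause the transfusion gap, which is the same in both documents.

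**Conclusion.** The concern holds as an ambiguity in grading a component of the primary endpoint. On the literal reading, the bleeds in the first table fall from major to minor and, if no other major criterion applies, leave the primary count. The direction favours non-inferiority. The effect on the result is confined to counts near the cut-off, which is 6 versus 7 of 75 at one-sided 0.025 and 7 versus 8 with a one-sided 95% bound.

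This rests on the plan's own 1 g/dL per unit, on 75 evaluable subjects, and on the asterisk being read where it is placed. The frequency of such bleeds is unknown, so the documents do not support the stronger inference that the trial's result will be biased. The different haemoglobin ranges are a consistency error with no effect on grading. The wording should be corrected, but the design is not undermined.

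**What to change.** In both documents, state that the haemoglobin drop used for endpoint grading is the measured drop plus 1 g/dL per unit transfused, and that it applies to both the major and the life-threatening thresholds. State that the primary endpoint is graded from these criteria and not from the label 3a. Reconcile the haemoglobin range for major bleeding between SAP 4.2 iv and the protocol.

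The cost is a few sentences in the definitions of each document. The small downside is that a few more bleeds may count as major.

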9.3.1 Subject withdrawal/exclusion

A patient is enrolled in the study by signing an Ethics Committee approved Informed Consent Form; if he/she meets all eligibility criteria (both pre-procedure and during the procedure) and there is intent to close the femoral artery puncture site using the PerQseal® and the PerQseal® closure device contacts the patient¹.

Patients on whom the PerQseal[®] closure device is not used due to failure to meet eligibility criteria/withdrawal of consent are considered not enrolled in the study. Patients not exposed to the PerQseal[®] closure device will not require additional post procedure, pre-discharge or post discharge follow-up assessments and will not be included in safety and performance analyses. For

¹ The PerQSeal® closure device is considered to have contacted the patient if the loading cannula of the PerQSeal® closure device is inserted into the Introducer sheath.

enrolled patients that have received exposure to the PerQseal[®] closure device, but the device was not deployed for reasons other than device failure their data will be included in safety, but not performance analyses and all post procedure, pre-discharge and post discharge follow-up assessments will be performed.

A patient may withdraw from the study at any time if he/she decides to do so. However, all data collected to the time of withdrawal will be recorded in the worksheet, with a note to indicate that the patient has withdrawn their consent to further participate in the study. No further follow-up or data will be recorded for that patient on the worksheet or eCRF. Note that routine management and standard practice of care should continue for the patient without prejudice.

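### SAP 9.3.1, read with the Device Failure definition in 4.2 viii, drops some non-deployed malfunctions from the technical-success denominator that 11.1 and 4.2 xiii keep as non-successes

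*SAP*

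**What the plan says.** Four parts of the SAP bear on a device whose deployment was attempted but not completed.

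- **4.2 viii (Device Failure)** has two conditions. The device must fail to provide percutaneous closure, with the failure "resulting in interventional (e.g. stent-graft) or surgical correction". It lists no exempt treatment.
- **9.3.1 (withdrawal/exclusion)** concerns enrolled patients exposed to the device. Where "the device was not deployed for reasons other than device failure their data will be included in safety, but not performance analyses".
- **4.2 xiii (Technical Success Rate)** puts in the numerator "closure devices that are deployed and achieve haemostasis" without need for "alternative treatment (other than manual compression or adjunctive endovascular ballooning) at target access site". The denominator is every device for which deployment was attempted. It adds: "Device malfunction resulting in alternative therapy will be considered as a technical failure".
- **11.1 (analysis populations)** defines the mITT set, from which 11.7 takes the performance proportion. A device prevented from deploying is removed only if the reason lies in the exclusion criteria or in the primary procedure.

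The minor-complication list in 4.2 iii, repeated in the protocol's Definitions, includes "Percutaneous closure device failure" with no ballooning exemption. The last item of the same list, on failure to achieve haemostasis, does exempt manual compression and adjunctive ballooning.

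**The concern.** The term that decides entry to the performance analyses in 9.3.1 is defined by the treatment that followed, not by what the device did. A device can therefore malfunction, remain undeployed and still not be a Device Failure, provided no interventional or surgical correction followed. Section 9.3.1 then removes the closure, while 11.1 retains it.

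Technical success is tested for non-inferiority against a limit of 0.81, so the denominator matters. Removing a non-success can only raise the observed rate and its lower bound. The study is single-arm and unblinded (SAP 8), so the choice between the two rules should not be left until the results are known.

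A smaller issue comes from the same definition. Because viii and the minor-complication item say nothing about ballooning, an adjudicator could count a ballooned closure as a minor complication although xiii makes it a technical success.

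**Working it through.** **1. One event under each rule.** Take a device whose deployment is attempted, which malfunctions and cannot be deployed, and where closure is managed without interventional or surgical correction (for example, by manual compression).

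| SAP section | Test applied | Result |
|---|---|---|
| 4.2 viii | Interventional or surgical correction followed? No | Not a Device Failure |
| 9.3.1, using viii | Not deployed, reason other than Device Failure | Out of the performance analyses |
| 11.1 / 11.7 | Exclusion criterion or primary-procedure reason? No | Stays in mITT |
| 4.2 xiii | Attempted: yes. Deployed: no | In the denominator, not in the numerator |

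The manual-compression exemption in xiii does not make this event a success, because the numerator requires a deployed device. Nor does the closing sentence of xiii on malfunction: it names one kind of failure and does not turn an undeployed device into a success.

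**2. Inputs for the size of the effect.**
- Limit: 0.84 − 0.03 = 0.81 (SAP 11.7).
- One-sided level 0.025 (SAP 10) and exact binomial interval (SAP 11.7).
- Closures: 75. This is an assumption of one closure per planned subject; SAP 10 gives 75 treated subjects, and bilateral closures would add to the count.
- Number of such malfunctions, k: not given; 1 to 3 assumed.

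Formula: the exact lower bound for x successes in n is the 0.025 quantile of Beta(x, n − x + 1). The test passes if the bound exceeds 0.81.

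**3. The plan's own figure.** SAP 10 states a minimum of 44 closures for performance with 90% power, but gives no expected success rate. With the exact method, 44 closures need 41 successes (bound 0.8134; 40/44 gives 0.7833). Power is 0.823, 0.902 and 0.958 for true rates of 0.95, 0.96 and 0.97. The first size to reach 90% power is 58, 44 and 36 respectively. So 44 is reproduced if 0.96 is assumed, but cannot be confirmed from the stated inputs. It does not settle the conflict.

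**4. Effect at 75 closures.** The test passes with at most 7 failures: 68/75 gives 0.8171 and 67/75 gives 0.8006. Let f be the number of other failures.

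| f | k | k kept as failures (11.1, xiii) | k dropped (9.3.1 with viii) |
|---|---|---|---|
| 7 | 1 | 67/75: 0.8006, fail | 67/74: 0.8148, pass |
| 7 | 2 | 66/75: 0.7844, fail | 66/73: 0.8124, pass |
| 7 | 3 | 65/75: 0.7684, fail | 65/72: 0.8099, fail |
| 6 | 1 | 68/75: 0.8171, pass | 68/74: 0.8318, pass |
| 6 | 2 | 67/75: 0.8006, fail | 67/73: 0.8296, pass |
| 5 | 3 | 67/75: 0.8006, fail | 67/72: 0.8453, pass |

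In every row the bound is higher when the closure is dropped. The conclusion changes only near the boundary.

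**5. Ballooning.** A deployed device that achieves haemostasis with adjunctive ballooning is a success under xiii and 11.7, neither of which uses the term Device Failure. For example, 70 successes that include three ballooned closures remain 70/75, bound 0.8512, whatever viii says. Only the minor-complication count can move, by 1/75 = 1.3 percentage points per closure. That endpoint is summarised in SAP 11.7 and Table 4, with no limit or test.

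**The case against.** **The analysis-population section governs.** SAP 11.7 takes the performance proportion from the mITT set, and 11.1 keeps device malfunctions in it. A reader of 9.3.1 alone might infer that the plan as a whole loses malfunctions from its denominator. The documents do not support that: 11.1 says the opposite. In addition, 9.3.1 writes device failure in lower case and may intend the ordinary sense, which would include a malfunction. Both points stand, and they make this a conflict between two rules and not a settled exclusion. They do not remove it, because the SAP defines the term and 9.3.1 expressly addresses performance analyses.

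**The event is narrow.** It requires an undeployed device at a large arteriotomy with no interventional or surgical correction. A malfunction that led to surgical repair meets viii and is retained even under 9.3.1. This stands; the frequency is unknown.

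**A consequence-based definition is not a contradiction in itself.** This also stands. The malfunction sentence in xiii likewise requires a consequence, and Table 13 reports malfunctions separately. The difficulty arises only because 9.3.1 uses the term as a gate.

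**Ballooning.** A reader might infer that a ballooned closure is a Device Failure, or that such closures could tip the technical-success test. Neither follows. Definition viii first requires failure to provide closure, its only interventional example is a stent-graft, and the SAP calls ballooning adjunctive. Such a closure may be classed as a Device Failure; the text does not say that it is. The technical-success test is unaffected.

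**Conclusion.** The point holds as an unresolved conflict over the denominator of the tested technical-success endpoint. SAP 9.3.1 read with 4.2 viii drops a non-deployed malfunction that had no interventional or surgical correction; 11.1 and 4.2 xiii keep it as a non-success. The first reading always favours the device. Near the boundary one closure is enough to reverse the conclusion, as the 67/75 and 67/74 comparison shows. This rests on 75 closures, the exact interval at one-sided 0.025, and an assumed one to three such events. Away from the boundary the conclusion does not change.

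The ballooning gap is real but minor. It leaves the descriptive minor-complication count open to two classifications and has no bearing on the non-inferiority test. The primary endpoint is not affected by either part. The definitions should be reconciled before the data are analysed.

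**What to change.** 1. **Amend 9.3.1 to match 11.1.** Only devices not deployed because of an exclusion criterion or a primary-procedure issue leave the performance analysis. Any attempted device not deployed because of the device itself stays in the denominator as a technical failure.
2. **For analysis, align 4.2 viii with xiii.** Device Failure means that deployment was attempted and either the device was not deployed because of the device, or haemostasis was not achieved without alternative treatment beyond the two kinds that xiii exempts. Malfunction alone should not be a criterion: a device that malfunctions but still deploys and seals without alternative treatment would then be both a failure and a technical success. Such events are reported in Table 13. Reconcile the device-failure item in the minor-complication list with this definition, in the SAP and in the protocol.
3. **Report ballooned closures as a separate count**, for example in Table 13.

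The cost is SAP wording plus a matching edit to the protocol's minor-complication definition. These are classification rules for analysis and do not alter patient management. The downside is that the reported technical success rate may be slightly lower if such malfunctions occur.
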